### 9.10. Data Analysis

#### 9.10.1. Qualitative Analysis

In the early stages of questionnaire development and validation – face and content validity, it seemed appropriate to seek the opinions and comments of healthcare professionals with expertise in the care of the older people and who are aware of the problem of polypharmacy and the importance of medication deprescription, as well as our target population – older adults and informal caregivers. In this respect, a qualitative methodology is appropriate for understanding the needs of users and care providers (Kohn & Christiaens, 2012). For the data analysis, the open-ended questionnaire responses concerning comments will be analyzed for common or contradictory information, which will be used to construct the guide for the FG. Full transcriptions of the FGs will be performed and an analysis of the corpus will be carried out by deductively identifying the units of analysis, which will be used for adjusting or eliminating items from the questionnaire.

#### 9.10.2. Statistical Analysis

To assess the psychometric properties of the questionnaire, an EFA will be performed. The aim of this study is to develop and validate a new measurement instrument, which is why we will use an exploratory method, as no a priori structure is known about the linear relationships between items and factors. (McCoach et al., 2013). Thus, using the EFA it will be possible to reduce data by exploring “... *the dimensionality of an instrument by finding the smallest number of interpretable factors needed to explain the correlations among set of items*” (McCoach et al., 2013).

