
Informal caregiver population:
 

• Caregiver age under 18 years old;

• Caregivers who are paid for the care they provide;

• Caregiver inability to give consent and complete a written questionnaire in French;

• Caregiver inability to understand and speak in French.

Procedures: Schedule of assessments – Study Flowchart

Statistical Considerations
 
Methods that will be used to validate the questionnaire: face validity, content validity, construct validity, internal validity and test-retest reliability.
 
To assess the psychometric properties of the questionnaire, an exploratory factor analysis (EFA) will be performed – construct validity. Face and content validity will be performed by qualitative methodology, and using the content validity ratio (CVR). Internal validity will be assessed using the Cronbach’s alpha and omega coefficient, and test-retest reliability will be investigated using the Cohen’s kappa and Interclass correlation coefficient (ICC). Logistic regression will be performed to investigate the association between the determinants and the intention, or deprescribing behavior.

**Development and validation of a health behaviour theory-based questionnaire to explore the willingness of older adults and informal caregivers to deprescribe (HBQtD)**

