#### *Study configuration*

The initial questionnaire was developed considering the results of a previous systematic review (article currently being written), which was intended to identify (concepts included in) behavioral health theories (HBTs) that explain older adults' and informal caregivers' deprescribing intention and/or their actual deprescribing behavior. This systematic review, revealed several main dimensions, such as goals intention to deprescribe, perceived risks about medication, self-efficacy towards deprescribing, subjective norms, social support to deprescribe, and finally opportunities for deprescribing. This systematic review, also showed that attitudes was already widely investigated, indeed four systematic reviews and two meta-analysis were already performed, synthesizing studies that have used PATD and the revised version (Seewoodharry et al., 2022; Oktora et al., 2022; Chock et al., 2021; Weir et al., 2021). As a result, the items of this initial questionnaire were developed according to the dimensions found in the systematic review, the main results of the systematic review focused on the rPATD and the Beliefs about Medicines questionnaire (BMQ), since a predictor of risk perception was beliefs about medication (Martin et al., 2013).

The initial version for informal caregivers was developed by modifying the wording of the items, in the version for the older adults, adapting them for informal caregivers.

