#### **1. Item Development process**

The conceptualization of the concepts used in the questionnaire was based on the results of the systematic review carried out previously. The items were built in relation to the most relevant constructs and predictors identified in the results of the systematic review, and some items from two different questionnaires (rPATD and BMQ) were also used to assess the components of some constructs, such as attitudes and perceived risk. The dimensions importance, in a first step were identified by discussion with the promotor in relation to the systematic review results. The questionnaire and items format were also discussed with the promotor, and a statistician from SMCS.

Some considerations have been taken into account in the item construction: “*Statements should be simple and short as possible, and the language used should be familiar to target respondents... Items should address only a single issue... Leading questions should be avoided, as they may bias responses. Items that all respondents would answer similarly should not be used, as they will generate little variance*” (Hinkin, 1998). In addition, items related to deprescribing behavior were regrouped and separated from those related to medication use.

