**4. Validation of the questionnaire – older adult and informal caregiver version**

The final item selection process will incorporate the results of the different qualitative analyses (interviews and FG) and quantitative analyses of the field trial data. This final version of the questionnaire will be then applied to a large sample size of older adults and informal caregiver for reliability validation.

This validity process “... refers to the degree to which evidence and theory support the interpretations of test scores for proposed uses of a test. Validity is, therefore, the most fundamental consideration in developing and evaluating tests” (AERA, APA, & NCME, 2014 cit by Clark & Watson, 2019). As a result, during this phase, a construct validity will be carried out, which is related to the “evaluation of the extent to which a measure assesses the construct it is deemed to measure” (Strauss & Smith, 2009). The internal consistency will be also calculated, as it reflects “the extent to which the questionnaire items are inter-correlated, or whether they are consistent in measurement of the same construct” (Tsang et al., 2017). Finally, a test-retest reliability will be performed, by repeating the administration of the same questionnaire with a small sample of participants (20 older adults and 20 informal caregivers) who have already completed the questionnaire. This process will ensure the consistency of questionnaire items responses across repeated administration (Tsang et al., 2017).

The two additional questionnaires (HLS19\_Q12 and MHLCS) will be administered to all participants (older adults and informal caregivers) in this final stage of the questionnaire validation process.

*Expected duration of subject participation*

Participants will be included throughout the questionnaire development and validation process, which will begin as soon as the ethics committee's opinion is received, and will continue until the sample size required for validation of the questionnaire is reached, in the final phase. The whole process is expected to take around 12 months.

*Planned timetable*

Activities/ Months	2023										2024						
	06	07	08	09	10	11	12	01	02	03	04	05	06	07			
Questionnaire development				15d	15d	15d	15d	15d	15d								
Ethics committee																	
Cognitive pre-test with OA and IC																	
Round with HCP																	
FG with HCP																	
Round with OA and IC																	
FG with OA and IC																	

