### *Psychometric proprieties of the questionnaire*

The appropriateness of the data factor analysis, considered “to be a variable describing how much an individual would score on a factor” (Yong & Pearce, 2013), will be assessed using the Kaiser-Meyers-Olkin test and Bartlett’s test of sphericity. Factors will be extracted using the Principal Axis Factoring, that is based on the notion “that all variables belong to the first group and when the factor is extracted, a residual matrix is calculated. Factors are then extracted successively until there is a large enough of variance accounted for in the correlation matrix” (Tucker & MacCallum, 1997 cit by Yong & Pearce, 2013). In addition, for a better interpretation of the factors, a rotation will be performed, more precisely an oblique rotation (Yong & Pearce, 2013). The number of factors to be retained will be determined using the Kaiser-Guttman criterion (retaining all factors that are above the eigenvalue of 1) and the scree test (retaining all factors that are above the point of inflexion in the scree plot). Loadings above 0.30 will be considered as significant, as “anything lower would suggest a really weak relationship between the variables” (Tabachnic & Fidell, 2007 cit by Yong & Pearce, 2013).

Another essential step in the creation of a questionnaire is to gather evidence of the score's reliability (E. Reeve et al., 2016). In reality, score reliability “is an indication of the consistency, stability, or precision of scores” (McCoach et al., 2013). Consequently, reliability focus on two types of measurement: internal consistency that estimate a “measurement error within the set of questions” (McCoach et al., 2013) and test-retest reliability estimates, that is a measurement error across two or more instrument administration (McCoach et al., 2013).

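### Items were written to named theory dimensions, but the plan fixes no expected item-to-dimension structure or failure criterion, so the planned factor analysis does not formally test those dimensions.

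*Combined protocol and SAP*

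**What the plan says.** Section 9.1 (Study configuration) reports that a systematic review yielded main dimensions, among them "goals intention to deprescribe, perceived risks about medication, self-efficacy towards deprescribing, subjective norms, social support to deprescribe, and finally opportunities for deprescribing", and that "the items of this initial questionnaire were developed according to the dimensions found in the systematic review". Step 1 of the study design (Item Development process) repeats this: "The items were built in relation to the most relevant constructs and predictors identified in the results of the systematic review". It adds that some rPATD and BMQ items were used for components such as attitudes and perceived risk.

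Step 4 (Validation of the questionnaire) defines construct validity as the "evaluation of the extent to which a measure assesses the construct it is deemed to measure". The synopsis gives that task to one method: "an exploratory factor analysis (EFA) will be performed – construct validity". Section 9.10.2 explains the choice: "we will use an exploratory method, as no a priori structure is known about the linear relationships between items and factors".

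Under Psychometric proprieties, the structural criteria are:
- the "Kaiser-Meyers-Olkin test" (no cut-off given) and Bartlett's test;
- principal axis factoring with oblique rotation;
- retention by eigenvalue above 1 and by scree test;
- loadings above 0.30.

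Alpha and omega have a 0.7 threshold, but the scales on which they are computed are not named. Logistic regression relates items to deprescribing intention or behaviour. The health literacy and locus of control questionnaires enter the analysis only as moderators.

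**The concern.** The primary objective is to validate a questionnaire based on health behaviour theory, and the absence of such theory is the plan's main criticism of the rPATD. An intended grouping of items must therefore exist, at least in the authors' own records, yet the analysis never uses it. The plan states no expected number of factors, no item-to-dimension table, and no result that would count as failure of the intended structure. If the data grouped the items quite differently from the theory, every structural criterion could still be met, and the plan has no rule for what may then be claimed about the theory constructs.

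**Working it through.** **Plan's own figures.** 5 + 10 + 30 + 300 = 345 per population, as stated. The 300 comes from cited rules of thumb (200 to 300) and cannot be derived. The first draft has 58 items for older adults and 55 for caregivers.

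**Step 1: what the criteria depend on.** Let R be the item correlation matrix, with n respondents and p items.
- KMO = Σr² / (Σr² + Σq²), over off-diagonal correlations r and partial correlations q obtained from R.
- Bartlett χ² = −[(n − 1) − (2p + 5)/6] · ln|R|.
- Eigenvalues, the scree plot and the rotated loadings are also computed from R.

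The dimension an item was written for appears in none of these. Reassigning items to other intended dimensions leaves each quantity exactly unchanged, whatever the true loadings.

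**Step 2: how this looks in numbers.** Simulation with n = 300, 58 five-point items, principal axis factoring, promax rotation, the eigenvalue rule and 100 data sets per row. Loadings of 0.6 and, where there are several factors, correlations of 0.3 are assumptions; the documents give neither.

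| True structure | Bartlett rejects | Mean KMO | Mean factors with eigenvalue > 1 | Items loading > 0.30 | Mean alpha, six intended scales |
|---|---|---|---|---|---|
| Six factors, as intended | 100% | 0.84 | 13.3 | 100% | 0.83 |
| Six factors, items assigned at random | 100% | 0.85 | 13.4 | 100% | 0.60 |
| Three factors unrelated to the intention | 100% | 0.90 | 11.8 | 100% | 0.67 |
| One general factor | 100% | 0.96 | 10.6 | 67% | 0.82 |
| Pure noise | 5% | 0.45 | 26.4 | 61% | about 0 |

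The first two rows cannot be told apart on the planned structural criteria. The third also passes, because no KMO cut-off or expected number of factors is set.

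**Step 3: agreement with the intended map.** This is the share of items whose largest pattern loading falls on the factor matched one-to-one to their own dimension. In separate runs of 40 to 60 data sets:
- six factors extracted: 100% if the map is right, 31% to 32% if it is wrong;
- eigenvalue rule: 94% if right, 30% if wrong.

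A wrong map scores about 30%, not 1/6 = 17%, because the matching picks the most favourable pairing. A pass mark has to allow for this.

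**Step 4: alpha depends on the scales chosen.** Computed on six EFA-derived factors, the lowest alpha averaged about 0.79 in both cases. Computed on the intended scales, mean alpha was 0.83 with the right map and 0.60 with the wrong one. In the latter case the lowest averaged 0.55 and was below 0.7 in every run. Alpha alone is not enough, however: with one general factor it is 0.82 on the intended scales although the dimensions are not distinct.

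**Step 5: sample use.** Halving the sample for separate exploratory and confirmatory analyses would leave 150 per half. That is 150/58 = 2.6 respondents per item, against 300/58 = 5.2 for the full sample, and is below the minimum of 200 that the plan cites.

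**The case against.** A reader might infer that no planned statistic can count against the theory and that construct validity cannot fail. The documents do not support that.
- Bartlett's test fails to reject in 95% of pure-noise data sets.
- Section 9.10.2 seeks interpretable factors, and interpretation draws on item content. A factor mixing unrelated self-efficacy, norm and risk items could be judged uninterpretable, although no rule governs that judgement.
- Alpha and omega have a threshold. Step 4 of the design describes internal consistency in terms of a shared construct, so computing them per intended dimension is an open reading. The plan places the ICC at the factor level, which points towards EFA-derived scales, but does not say so for alpha.
- The logistic regression could show that theory-based items are unrelated to intention or behaviour. That is criterion evidence, not structural evidence, but it bears on the theory.

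Nor do the documents support the inference that inconvenient factors would simply be renamed afterwards.

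The inconsistency is also softer than it first looks. The sentence in section 9.10.2 concerns relationships between items and factors, and writing items to concepts does not make their factor structure known. The list of dimensions is illustrative, attitudes are added, and items will be dropped or reworded before validation. EFA is defensible for a new tool, and the secondary objectives openly name it. The appended questionnaires were not available for this review, so whether they group items by dimension could not be checked.

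What stands is that, in the text available, nothing connects the intended dimensions to the analysis. The healthcare professionals' ratings do not fill this gap: they concern whether each item belongs in the questionnaire, not whether it fits a particular construct.

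**Conclusion.** The concern holds in this limited form: the structural part of the construct-validity analysis does not formally test whether items measure the constructs they were written for, because no expected structure or failure criterion is pre-specified. That the planned structural criteria ignore the intended dimensions follows from their formulas and needs no assumption. The size of the contrast (100% against about 31% agreement, with identical loading results) rests on loadings of 0.6, factor correlations of 0.3, six factors, no cross-loadings and the 58-item first draft. Real data will be less clean and the final item set may be smaller. The choice of EFA is not at fault. This should be changed before the validation data are opened, because a map drawn up afterwards would carry little weight.

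**What to change.** Keep the EFA on all 300 per version, and:
1. Reword section 9.10.2 to say that dimensions were intended when the items were written but that their factor structure is untested.
2. Before the validation data are opened, freeze a table for each version assigning every retained item to its intended dimension, attitudes included.
3. Report the share of items whose largest pattern loading falls on the factor matched to their own dimension. Fix the matching rule and the pass mark in advance, with the mark well above the roughly 30% that a wrong map can reach.
4. Compute alpha and omega on the intended scales as well as on the EFA-derived factors, using the existing 0.7 threshold.
5. State that, if these checks fail, the structure will be reported as data-derived and not as validation of the theory constructs.

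A confirmatory factor analysis of the frozen map on the same data is optional support. Its form depends on the final items: six factors on 58 items would give 58 × 59/2 − (2 × 58 + 15) = 1580 degrees of freedom, but that assumes six dimensions and the first draft.

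The cost is one table per version and a few lines of analysis, with no new participants. The downside is that the result can be unfavourable.

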**3. PROTOCOL SYNOPSIS**

Name of Sponsor UCLouvain (ARC, Actions de Recherche Concertée – Di-Prescribe)
Title of Study Development and validation of a health behavior theory-based questionnaire to examine the willingness of older adults and informal caregivers to deprescribe
Service(s) in which the experimentation is taking place Primary care setting, nursing homes in Brussels and Wallonia
Publication (reference)
Studied period : September 2023 to october 2024
Objectives: - Primary: to develop and validate a health behavior theory-based questionnaire to examine the older adults’ and informal caregivers’ determinants of deprescribing behavior - Secondary: assess the psychometric properties of this new instrument
Hypotheses The use of health behavioral constructs in the development of an assessment tool will have greater predictive validity than that of existing tools
Study Design Questionnaire development and validation that involve an item development and validation stage
Number of planned patients: - 345 older adults; 345 informal caregivers
Main criteria for inclusion (inclusion/exclusion criteria) Inclusion criteria: Older adult population: 
 
• Age 60 years or older;
 
• Taking at least 5 medications daily;
 
• Having at least one chronic condition;
 
 Informal caregiver (such as spouse, family/ friend caregivers): 
 
• Self-identified as a caregiver of an older adult who has 60 years old or older, that are taking at least 5 medications daily and having one or more chronic condition;
 
• The care recipient lived in the community or in a nursing home.
 
 Exclusion criteria: Older adult population: 
 
• Suffering from psychiatric trouble;
 
• Past or present drug or alcohol dependency;
 
• Having a terminal illness;
 
• Inability to complete a written questionnaire in French due to a functional or cognitive impairment;
 
• Inability to understand and express oneself in French.
 

**Development and validation of a health behaviour theory-based questionnaire to explore the willingness of older adults and informal caregivers to deprescribe (HBQtD)**

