## **3. Pre-test of the questionnaire – older adult and informal caregiver version**

Once the final version of the questionnaire developed, it will be administered to a small group of participants, generally 10% of the sample size required to perform an EFA (Aithal & Aithal, 2020). It will be asked to the older adults and to the informal caregivers to complete the questionnaire and to provide any comments about the way items have been written and on items comprehension. This pilot study will help to assess the clarity of the items and to remove irrelevant items.

In this validation step will also be administered the HLS19\_Q12 and MHLCS.

**Development and validation of a health behaviour theory-based questionnaire to explore the willingness of older adults and informal caregivers to deprescribe (HBQtD)**

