#### *Sample Size*

According to Yong & Pearce (2013), EFA performs better with a larger sample size, as it reduces the error in the data. However, no formal sample size calculation is available for EFA, some authors recommend at least 200 participants (McCoach et al., 2013), while others put the targeted figure at 300 (Yong & Pearce, 2013). So, in this study, we are targeting a sample of 300 older adults and 300 informal caregivers. For the test-retest reliability, a sample size of 20

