The most commonly used estimated of internal consistency is Cronbach’s coefficient alpha ( $\alpha$ ; (McCoach et al., 2013)). Nevertheless,  $\alpha$  is predicted on several assumptions, that are not always respected (Trizano-Hermosilla & Alvarado, 2016; McCoach et al., 2013), which is why the omega coefficient ( $\omega$ ; (McDonald, 1999)) will also be used, as an alternative to  $\alpha$  (Doval, 2023; Trizano-Hermosilla & Alvarado, 2016). In reality, a number of researchers showed that  $\omega$  is a more sensible index, with lower risk of over- or underestimating reliability (Dunn et al., 2014). Therefore, the reliability coefficient range between 0 and 1, and a value above 0.7 will be considered as good internal consistency, while a value above 0.90 will be considered as excellent (Koo & Li, 2016).

According to Koo & Li (2016) “A more desirable measure of reliability should reflect both degree of correlation and agreement between measurements”, that’s why the intraclass correlation coefficient (ICC) will be used to evaluate test-retest reliability at the factor level, and linear-weighted Cohen’s Kappa and percent agreement at the individual item level. These measurements have been used to validate other instruments such as rPATD (E. Reeve et al., 2016) and the rPATD version for BZDs (Péteïn et al., 2023). The ICC classified the reliability

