## **Development and validation of a health behaviour theory-based questionnaire to explore the willingness of older adults and informal caregivers to deprescribe (HBQtD)**

as poor (<0.50), moderate (0.50-0.75), good (0.75-0.90) and excellent (>0.90) (Koo & Li, 2016). The Cohen's Kappa nomenclature classify the strength of agreement also as poor (<0.00), slight (0.00-0.20), fair (0.21-0.40), moderate (0.41-0.60), substantial (0.61-0.80) and almost perfect (0.81-1.00) (Landis & Koch, 1977).

All numerical variables will be described using means, medians and standard deviation, whereas all categorical variables will be described using frequencies and proportion. A logistic regression analysis will be performed to better understand the association of items from the questionnaire and intention, or actual deprescribing behavior. The moderating influence of HL and locus of control on the effect of the determinants on deprescribing intention or behavior will be checked via moderation analysis using bootstrapping. Statistical analysis will be conducted using SPSS Statistics version 1.0.0.1406, and a type I error rate of <0.05 will be considered significant.

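### One sample of 300 per version is used to find the factor structure, grade reliability and fit the logistic regression, so the structure is never confirmed in other respondents and apparent predictive performance is optimistic

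*Combined protocol and SAP*

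**What the plan says.** **Sample.** Section 9.10.2 (Sample Size): "we are targeting a sample of 300 older adults and 300 informal caregivers". The figure is a rule of thumb: "no formal sample size calculation is available for EFA, some authors recommend at least 200 participants", and others are cited for 300. The Synopsis gives "345 older adults; 345 informal caregivers" in all. The only earlier quantitative administration of the completed questionnaire is the pre-test (Section 9.1, step 3), sized at "generally 10% of the sample size required to perform an EFA", which is 30 per version.

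**Use of the 300.** Section 9.10.2 chooses an exploratory method because no structure is known beforehand: "Thus, using the EFA it will be possible to reduce data by exploring" dimensionality, in a sentence that goes on to speak of the fewest interpretable factors. Factors are retained by the Kaiser-Guttman criterion and the scree test, and loadings above 0.30 count as significant. For alpha and omega, "a value above 0.7 will be considered as good internal consistency", and above 0.90 is excellent. Then: "A logistic regression analysis will be performed to better understand the association of items from the questionnaire and intention" or actual behaviour. Bootstrapping is planned only for the moderation analysis.

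**Status of the questionnaire given to the 300.** Section 9.1, step 3, removes irrelevant items at the pre-test. Step 4 bases the last item selection partly on data from a field trial that it does not identify, and then says: "This final version of the questionnaire will be then applied to a large sample size of older adults and informal caregiver for reliability validation".

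**Purpose.** The primary objective (Section 9) is both to develop and to validate the instrument. The hypothesis (Synopsis and Section 8) is that it will have greater predictive validity than existing tools.

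**The concern.** A structure first found in 300 people cannot also be confirmed by them. Test-retest does not fill the gap: it repeats the questionnaire in 20 + 20 people who have already completed it, so it addresses stability over time and not structure. The pre-test of 30 cannot support an EFA of up to 58 items.

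The regression has a separate problem. It is worded at item level, with 58 items for older adults and 55 for caregivers (Section 9.1, Method for data collection), and is fitted and read in the same respondents. With so many candidate predictors, apparent discrimination can look strong when there is none. Because the hypothesis concerns predictive validity, uncorrected performance would favour it.

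At stake are the claim that the questionnaire has been validated and any statement that it predicts intention or behaviour well.

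**Working it through.** **1. The plan's own figures.** 5 + 10 + 30 + 300 = 345 per version and 10% × 300 = 30. Both reproduce.

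**2. Information for the regression.** The plan gives no expected outcome rate. As an assumption I use the two rates that Section 7 (Screening Tools) reports from a cited study: 86% willing and 41% successfully deprescribing.

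- Minority-outcome respondents: 300 × (1 − 0.86) = 42; 300 × 0.41 = 123.
- Per item, 58 items: 42/58 = 0.7; 123/58 = 2.1.
- Per item, 55 items: 42/55 = 0.8; 123/55 = 2.2.
- Per scale with 7 scales: 42/7 = 6.0; 123/7 = 17.6.

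**3. Optimism in the c-statistic.** Monte Carlo, 80 data sets per row. Assumed settings: 58 five-point items, 7 factors (the six dimensions listed in Section 9.1 plus attitudes) correlated 0.3, loadings 0.3 to 0.7, principal axis factoring with promax. Where there is a true effect, three factors each have a log odds ratio of 0.4 per SD. Each cell shows the value in the same 300, the value in 4,000 new respondents, and the optimism (taken before rounding).

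| Rate, true effect | 58 items together | 7 scales fixed in advance | 7 scales built by EFA on the same data |
|---|---|---|---|
| 86%, none | 0.849, 0.497, 0.352 | 0.621, 0.499, 0.122 | 0.619, 0.499, 0.120 |
| 86%, present | 0.892, 0.592, 0.300 | 0.734, 0.675, 0.059 | 0.729, 0.677, 0.052 |
| 41%, none | 0.757, 0.499, 0.257 | 0.585, 0.503, 0.081 | 0.583, 0.500, 0.083 |
| 41%, present | 0.819, 0.615, 0.204 | 0.708, 0.681, 0.028 | 0.711, 0.681, 0.030 |

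The last two columns differ by at most 0.059 − 0.052 = 0.007. Building the scales on the same data adds nothing material. The number of predictors drives the optimism.

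**4. Can a bootstrap repair it?** Under assumed settings:

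- Scale scores: 0.688 apparent, 0.636 corrected, 0.628 in new respondents. This is adequate.
- 58 items, no true effect, 86% rate: 0.876 apparent, 0.668 corrected, 0.494 new. The bootstrap removes 0.876 − 0.668 = 0.208 of an optimism of 0.876 − 0.494 = 0.382, so the corrected value still misleads.

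**5. Optimism in alpha.** 60 data sets per row, the same 300 against 3,000 new respondents. An assumed rule keeps items whose largest loading exceeds 0.30.

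| Loadings | Factors extracted (7 true) | Same 300 | New | Optimism | Of scales above 0.7, share below 0.7 in new respondents |
|---|---|---|---|---|---|
| 0.5–0.8 | 7 | 0.840 | 0.840 | 0.000 | 0% |
| 0.3–0.7 | 7 | 0.707 | 0.698 | 0.009 | 17% |
| 0.3–0.7, 10 noise items | 7 | 0.668 | 0.658 | 0.010 | 30% |
| 0.2–0.5, 10 noise items | 7 | 0.454 | 0.361 | 0.093 | none pass |
| 0.5–0.8 | 11.8 (Kaiser alone) | 0.837 | 0.838 | −0.001 | 0% |
| 0.3–0.7, 10 noise items | 20.9 (Kaiser alone) | 0.650 | 0.624 | 0.026 | 30% |
| 0.2–0.5, 10 noise items | 24.3 (Kaiser alone) | 0.419 | 0.278 | 0.141 | none pass |

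For scale, Feldt's 95% interval is 1 − (1 − α)F, with F the 97.5% and 2.5% points on n − 1 and (n − 1)(k − 1) degrees of freedom. For α = 0.70, n = 300 and k = 8 it is 0.65 to 0.75. Much of the last column is therefore ordinary sampling error. Omega was not simulated.

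**6. Independent confirmation.** Splitting the sample gives 150 + 150, below the 200 that the plan cites, and 150/58 = 2.6 respondents per item instead of 300/58 = 5.2. A new sample of 200 to 300 would raise each version from 345 to between 545 and 645.

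**The case against.** The other side has four good arguments.

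- **Item deletion.** A reader might infer that items are dropped on the 300 and that a shortened questionnaire is then reported as validated. The documents do not establish this. The data reduction in Section 9.10.2 is a reduction to factors, no rule deletes an item after the EFA, and step 4 describes what the 300 receive as final. The unidentified field-trial data leave an ambiguity, no more.
- **Cause of the regression optimism.** A reader might also infer that EFA selection makes the items look more predictive. The EFA does not use the outcome, and the comparison with scales fixed in advance shows no material effect.
- **Reliability.** With moderate or good items and the right number of factors the bias in alpha is at most about 0.01, well inside its sampling error. The larger values need weak items or over-extraction. The plan pairs the Kaiser criterion with the scree test, so the Kaiser-only rows are an extreme case, although the plan does not say what happens if the two disagree.
- **No c-statistic is planned.** The regression is presented as a study of associations, and the plan does not say whether items enter together or singly. If singly, the problem is multiplicity: 58 × 0.05 = 2.9 false positives expected if no item is associated with the outcome.

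All four narrow the point. They do not remove it: no step checks the structure outside the data that produced it, and a hypothesis about predictive validity rests on an item-level model with no validation.

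**Conclusion.** The concern holds in a limited form. The structure will be unconfirmed, and that follows from the documents alone. The regression, if items are entered together, will be badly overfitted: optimism in the c-statistic is 0.20 to 0.35 with 58 items, against 0.03 to 0.12 with seven scales. These sizes rest on the assumed outcome rates, factor model and loadings.

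It would go too far to call the planned alpha and omega materially biased. For alpha that is true only with weak items or too many factors. For omega there is no calculation, though the same direction is expected.

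Section 9.1, steps 3 and 4, and Section 9.10.2 must be reconciled on whether any item is removed using the 300.

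**What to change.** **Section 9.10.2**

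- Keep the EFA on all 300 per version.
- Replace the item-level logistic regression with one on the factor (scale) scores. Report its bootstrap optimism-corrected c-statistic and calibration slope. Item-level associations become descriptive. A bootstrap of the 58-item model would not be enough (step 4 of the working).
- Report confidence intervals for alpha and omega beside the 0.7 and 0.90 grades.
- As a sensitivity analysis, fix the number of factors at the value retained in the full sample and report, for each item, the share of bootstrap resamples in which it stays on its factor. Fixing the number avoids a scree judgement in every resample.

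**Section 9.1, steps 3 and 4, with Section 9.10.2.** Say which data the last item selection uses and whether items can be deleted after the EFA.

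**Synopsis and Section 9.1, step 4.** Describe the product as developed and internally validated, with structure and predictive validity not yet confirmed in independent respondents. The bootstrap does not supply that confirmation.

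**Cost.** Some wording and extra scripted analysis, with no added participants. The reported figures and the validation claim become slightly less favourable.
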